Analysis Strategy: This study is a two-group, two-site randomized controlled trial. Primary effects of interest are greater CBT understanding and skills acquisition (Primary Aim 1) and lower levels of depression symptoms (Primary Aims 2a and 2b) in the CBT-D+ group compared to CBT-D alone. Secondary effects are lower comorbid diagnosis symptoms (i.e., lower psychological adjustment and reintegration problems, greater functional capacity, and quality of life, and lower levels of anger, PTSD, and anxiety (see table 8).

Independent variables: Randomized treatment group assignment (CBT-D+ versus CBT-D alone).

Dependent Variables: The primary outcomes on which the analysis is powered are CBT understanding and skills acquisition assessed by patient and therapist SoCT and depressive symptoms assessed by PHQ-9.

Sample Size Justification: The proposed sample size of 268 randomized (134 per group) was estimated based on the expected effect sizes to test hypotheses for the primary aims (Hypotheses 1 and 2[a,b]); adjustment of the testwise significance level to .01 for CBT understanding and skill acquisition (as measured by patient and therapist SoCT total scores) (Primary Aim 1) and depressive symptoms (measured by PHQ-9) (Primary Aims 2a and 2b) to limit inflation of type 1 error due multiple testing of hypotheses at 12-weeks post-therapy initiation and 6-months post-therapy; and anticipated attrition at 6-months post-therapy⁷ recommend clinically meaningful effect sizes of 0.50 (in terms of a standardized mean difference, d) when comparing alternative treatments in comparative psychotherapy research. When using the patient and therapist SoCT total scores to measure patient's CBT understanding and skill acquisition, standard deviations (SD) of ~0.72 and ~0.80 have been reported post-therapy by patients and therapists, respectively⁹³. Given these results, clinically meaningful effects of at least $d=0.50$ (or at least 0.36-point and 0.40-point differences in treatment group means assuming SDs of ~0.72 and ~0.80 for SoCT total scores from patients and therapists, respectively) may be detected with 0.80 power with 192 total (96 per group) when comparing mean SoCT total scores from patients and therapists between treatment groups based on linear contrasts from linear mixed model at testwise significance level of .01 (Hypothesis 1).

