Regarding Primary Aims 2a and 2b, standard deviations on the order of ~4.0 have been reported for PHQ-9 total scores post-therapy⁸. With minimum group sizes of 96 (192 total), we would have .80 power to detect clinically meaningful differences as small as $d=0.50$ (or at least a 2.0-point difference in treatment group means assuming a SD of 4.00) when comparing mean depressive symptoms (as measured the PHQ-9 total scores) between treatment groups at 12-weeks post-therapy initiation (Hypothesis 2a) and at 6-months post-therapy (Hypothesis 2b) at testwise level of significance of .01.

Although efforts will be made to retain participants through 6-months post-therapy, some attrition may occur. Research in CBT for depressive symptoms and the use of technology/apps to enhance treatment effects support at most 20% attrition at 12-weeks post-therapy initiation⁹ and an additional 8% attrition at 6-months post-therapy¹⁰ for an overall attrition rate of 28% at 6-months post-therapy. To ensure an adequate number of participants with full follow-up, we plan to enroll 134 per group (268 total), to conservatively adjust for overall attrition of 28% at 6-months post-therapy.

Data Analysis: Data will be analyzed using SAS⁹⁴ to conduct exploratory data analyses, missing data estimation, and repeated measures modeling for Primary Aims 1, 2a and 2b and Secondary Aim 2. MPlus⁹⁵ will be used for mediational analyses of Secondary Aim 1. While directional hypotheses have been posited, the level of statistical significance will be set conservatively at .01 to limit type 1 error inflation due to hypothesis testing at multiple outcomes and at multiple time points. Confidence intervals for point estimates will be computed at 99%.

Preliminary Analyses: Exploratory analyses will first be performed involving data description and screening for anomalies (e.g., outliers, nonnormality, missing data) with these results being used to 1) describe univariate/bivariate data distributions; 2) identify treatment

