The primary outcome variable for this aim is CBT understanding and skill acquisition (as measured by the patient and therapist SoCT total scores) assessed at baseline prior to randomization, completion of the acute phase of treatment (12-weeks post-therapy initiation), and 6-months post-treatment. Linear mixed modeling will be used to examine the overall efficacy of CBT-D+ on patient's CBT understanding and skill acquisition from both the patient's and therapist's perspectives over time. When fitting models to each of these dependent variables, time will be treated as fixed, categorical, repeated within-subject factor, while randomized treatment assignment (CBT-D+ vs. CBT-D alone) will be a fixed, categorical, between-subject factor, with interactions between time and randomized treatment assignment. In addition to the baseline value of the SoCT total scores, time-invariant and/or time-dependent covariates may be included to adjust for treatment group imbalances or variables related to the dependent variables of interest. In keeping with linear mixed modeling, random effects for participants will be included as well as possible random site effects. Standard fit indices will be used to identify the best-fitting variance-covariance structure for the repeated measures. We will also consider time as a continuous variable through the use of mixed effect regression models to accommodate individual deviations from the average trends. F-tests will be used to test the main effects and interactions included in the model. For each model, residual analyses will be used to identify possible model misspecification, outliers and influential cases. Sensitivity analyses will be performed to discern the impact of influential observations on results. To test hypotheses for Primary Aim 1 (Hypothesis 1) by formulating linear combinations of the model parameters from the fitted model, group comparisons between CBT-D+ and CBT-D alone will be performed at a) 12-weeks post-therapy initiation and b) 6-months post-therapy. Effect size indices with confidence intervals will be reported for the overall effect of the addition of CBT MobileWork V to CBT-D and at each time point of interest. Lastly, we will also explore possible modification of the treatment effect by participant characteristics (e.g., sex, age, etc.).

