Analysis Plan for Secondary Aim 1: We will explore CBT skills practice (as measured by the Assignment Compliance Rating Scale and the number of homework assignments completed) and acquisition of additional CBT skills (as measured by the SoCT P & T) as intermediate outcomes that may mediate the effect of the addition of CBT MobileWork-V to CBT-D on the distal outcome of depressive symptoms. Initially, we will fit simple mediational applying the change score method and estimate whether the effect of the addition of CBT MobileWork-V (predictor) on changes in depressive symptoms (outcome) is mediated through changes in the suspected mediators of CBT skills practice and acquisition of additional CBT skills. In addition to the chi-square goodness of fit statistic, standard summary fit indices (e.g., root mean square error of approximation, comparative fit index) will be used to assess the fit of the mediational model to the data, followed by model assessment via residual analyses. Total, indirect and direct effects will be estimated and reported with confidence intervals. If nonnormality is encountered, robust estimation methods (e.g., robust maximum likelihood estimation) will be used, or resampling approaches with the percentile bootstrap will be applied. Depending on the results from simple mediational modeling, we may also combine mediators and incorporate additional potential mediating/moderating variables (e.g., the number of CBT therapy sessions completed) into a multiple-mediator model to develop a more comprehensive picture of the possible pathways. Additionally, we will explore CBT skills practice and acquisition of additional CBT skills as mediational processes on depressive symptoms as an outcome process using parallel process latent growth curve modeling, where the mediational process is modeled by relating the randomized treatment group assignment (CBT-D+ vs. CBT-D) and the latent growth factors of the two parallel processes.

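### The initial mediation model uses change scores and does not prespecify baseline SoCT and PHQ-9 as covariates: this loses precision in the SoCT and PHQ-9 app contrasts and rests the skill-to-mood path on an unstated assumption

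*Combined protocol and SAP*

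**What the plan says.** Under Analysis Plan for Secondary Aim 1, the first mediation analysis is set out as: "Initially, we will fit simple mediational applying the change score method and estimate whether the effect" of adding the app on change in depressive symptoms passes through change in skills practice and change in skill acquisition. No baseline covariate is named and no change window is given. Multiple-mediator models may follow, depending on the results, and a parallel process latent growth model is also planned.

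The Aim 1 and Aim 2 plans show that SoCT and PHQ-9 are both measured at baseline before randomization. The Aim 1 model does name a baseline term: "In addition to the baseline value of the SoCT total scores", further covariates may enter. Preliminary Analyses adds that covariates and confounders, unnamed, will be brought in secondarily.

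The other mediators in Secondary Aim 1 are the Assignment Compliance Rating Scale (ACRS) and the homework count. Both arise during therapy, and no pre-randomization value is described for either.

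**The concern.** A change score carries minus its own baseline. This has two consequences.

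- **Randomized contrasts** (app to SoCT, and the total effect on PHQ-9). The change score is unbiased, but it fixes the weight on baseline at 1. A regression on baseline estimates that weight and is more precise unless the baseline-to-follow-up correlation is close to 1. The direct effect shows a similar precision loss, although it is not protected by randomization alone.
- **The skill-to-mood path.** Randomization does not protect it. If patients who start worse on both scales improve more on both whatever the app does, the two changes correlate even when skill has no effect on mood. The analysis would then lean toward mediation, the trial's title question and its hoped-for answer.

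**Working it through.** **Inputs from the documents.** Testwise alpha .01 ("the level of statistical significance will be set conservatively at .01 to limit type 1 error inflation"); effect "clinically meaningful differences as small as $d=0.50"; evaluable sample ("may be detected with 0.80 power with 192 total (96 per group"); PHQ-9 SD ("standard deviations on the order of ~4.0 have been reported for PHQ-9 total scores post-therapy"). **Assumed, because the documents give no value:** baseline-to-follow-up correlation r = 0.3, 0.5, 0.7; equal SDs at both visits; baseline SoCT–PHQ-9 correlation of −0.3 to −0.5; app effect on SoCT of 0.5 SD.

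**1. The plan's own sample size.** Two-sided, n per group = 2(2.576 + 0.842)²/0.50² = 93.5, so 94 by the normal approximation. The noncentral t gives power 0.799 at 95 and 0.805 at 96, so 96 per group reproduces. A one-sided test needs only 81, so the calculation was two-sided. For attrition, 96/(1 − 0.28) = 133.3, so 134. These figures concern the primary contrasts; none is given for mediation.

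**2. Precision of the app contrasts.** In SD units, √(2/96) = 0.1443.
- Change score: SE = √(2(1 − r)) × 0.1443
- Baseline-adjusted: SE = √(1 − r²) × 0.1443
- Variance ratio: 2(1 − r)/(1 − r²) = 2/(1 + r)

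| r | SE change | SE adjusted | Excess SE | Power, change | Power, adjusted |
|---|---|---|---|---|---|
| 0.3 | 0.171 | 0.138 | 24% | 0.628 | 0.847 |
| 0.5 | 0.144 | 0.125 | 15.5% | 0.805 | 0.918 |
| 0.7 | 0.112 | 0.103 | 8.5% | 0.968 | 0.987 |

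Power is for a single contrast of d = 0.50 at two-sided .01, not for the indirect effect. In PHQ-9 points (× 4.0), the SE falls from 0.683 to 0.551, from 0.577 to 0.500 and from 0.447 to 0.412. In simulated data over the same range of r, leaving out both baselines raised the SE by about 9–24% for the app-to-SoCT path, 7–25% for the total effect and 8–27% for the direct effect. The SE of the skill-to-mood path hardly changed.

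**3. Skill-to-mood path, true effect zero, two data models.**

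*Lagged model.* Each follow-up is r times its own baseline plus independent error, and the baselines correlate at ρ. Within arm, the changes have covariance (1 − r)²ρ and variance 2(1 − r), so the change-score slope is (1 − r)ρ/2.
- r = 0.5: 0.25ρ, that is −0.075 at ρ = −0.3 and −0.125 at ρ = −0.5.
- r = 0.3: 0.35ρ, that is −0.105 and −0.175.
- The adjusted slope is 0.
- False mediation (app-to-SoCT and skill-to-mood paths both p < .01) at r = 0.5 occurs in about 4% to 16% of simulated trials over this range of ρ, against about 1% with adjustment.
- At ρ = 0 there is no bias under the null.

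*Stable-trait model.* Each scale is a fixed personal level plus independent error at each visit, and the cross-correlation c is the same at every visit. The changes no longer contain the trait, so the change-score slope is 0. The adjusted slope is c(1 − r)/(1 + r − 2c²).
- r = 0.5, c = −0.3: −0.15/1.32 = −0.114. False mediation is about 13–15%, against about 1% for change scores.
- r = 0.7, c = −0.5: −0.15/1.20 = −0.125. False mediation is about 20%.
- r = 0.5, c = −0.5: −0.25/1.00 = −0.25, about 77%. This is a limiting case, because the traits would then correlate at −0.5/0.5 = −1.

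**4. When the skill effect is real.** In the lagged model with a true slope of −0.30, the change-score slope ran from −0.15 to −0.33 across r = 0.3–0.7 and baseline correlation 0 to −0.5. It is mostly attenuated, so the bias is not always toward mediation.

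**The case against.** The strongest objection is that choosing between change scores and baseline adjustment is a recognised analytic judgement, and the adjusted model can commit the same error. This stands for the skill-to-mood path. A reader might infer that the change-score model will manufacture mediation and should be replaced outright. The documents do not support that: they give neither the data model nor either correlation, and under stable shared traits the change score is the unbiased estimator.

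Other points against:

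- **Change windows.** The 4–16% applies when both changes run over the same interval. If SoCT change runs from baseline to 12 weeks and PHQ-9 change from 12 weeks to 6 months, the lagged model at r = 0.5 gives 2.2–3.7%. This stands, as the plan fixes no windows.
- **Which paths.** A reader might take the precision loss to cover every path from the app. It does not: with no described baseline for the ACRS or homework count, the app-to-practice path has no own-baseline gain.
- **Other provisions.** The latent growth model can represent starting level through its intercepts, and nothing forbids baseline covariates. But the plan does not say whether slopes are regressed on intercepts, and the secondary covariates are unnamed. Neither provision secures adjustment of the initial model.
- **Stakes.** The aim is exploratory and has no power statement, and at r = 0.5 the change score still reaches the design's 0.80. That limits the weight of the point; it does not justify giving up precision that costs nothing.

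**Conclusion.** The point holds in two parts of different strength.

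The precision loss in the SoCT and PHQ-9 app contrasts is firm. The standard error of a single contrast is about 8.5% to 24% larger than it need be for r between 0.7 and 0.3, assuming equal SDs and 192 completers. Adjusting the randomized app-to-SoCT path leaves it unbiased under either data model, so this is a free improvement.

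The skill-to-mood path is conditional. With a true effect of zero, the change-score slope is biased toward mediation if baseline level drives later change and the two baselines correlate. The adjusted slope is biased toward mediation if the scales share stable additive traits. Both arms receive twelve CBT sessions, so larger gains where there is more room are plausible, but that is a judgement and the documents do not decide it. They therefore do not support a statement that baseline confounding is present. Nor does anything here touch the primary analyses: the total effect of the app is unbiased either way because of randomization.

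**What to change.** In the Secondary Aim 1 section of the SAP:

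1. Prespecify baseline SoCT and baseline PHQ-9 as covariates in the SoCT mediator equation and in the PHQ-9 total-effect and outcome equations. With a scale's own baseline in the model, the arm coefficient is the same whether the dependent variable is follow-up or change.
2. Report the change-score estimates of the skill-to-mood path and the indirect effect alongside the adjusted ones, with the assumption behind each.
3. Claim mediation through skill only if both agree. The rate of joint false claims cannot exceed the smaller of the two separate rates, which is about 1% under either data model above. Agreement is still not proof, because both mechanisms could operate together.
4. State that this does not apply to the ACRS and homework-count mediators.

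The cost is SAP wording and one extra model, with no new data, plus a somewhat stricter condition for claiming mediation.

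### Secondary Aim 1 names no mediator-outcome confounders and plans no sensitivity analysis for unmeasured common causes of change in the mediator and change in PHQ-9

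*Combined protocol and SAP*

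**What the plan says.** Under Statistical Analysis, the Analysis Plan for Secondary Aim 1 explores skills practice (the compliance rating scale and the count of completed homework) and skill acquisition (patient and therapist SoCT) as possible mediators of the app's effect on depressive symptoms. Simple mediation models on change scores will "estimate whether the effect of the addition of CBT MobileWork-V (predictor) on changes in depressive symptoms (outcome) is mediated through changes in the suspected mediators". "Total, indirect and direct effects will be estimated and reported with confidence intervals". A multiple-mediator model and parallel-process growth models may follow.

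The checks named there are chi-square, RMSEA, CFI and residual analysis, with robust maximum likelihood or the bootstrap if data are nonnormal. Number of sessions completed appears only as an optional further mediator or moderator.

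Three statements elsewhere bear on the point:
- Preliminary Analyses, which is not limited to one aim, says that suspected covariates or confounders will be looked for, added secondarily, and their effect on results assessed. It names none.
- The Analysis Plan for Primary Aim 1 has an instrumental-variable analysis for treatment adherence and a sensitivity analysis for influential observations.
- Data Analysis states that "the level of statistical significance will be set conservatively at .01 to limit type 1 error inflation" and that intervals are at 99%.

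**The concern.** Randomization protects the effect of the app on the mediator and the total effect of the app on PHQ-9. It does not protect the slope of PHQ-9 change on mediator change. A factor that arises during treatment and moves both (motivation, a life event, a medication change, the working relationship with the therapist) creates such a slope even if skills do nothing for mood. Multiplied by a real app effect on skills, the slope is reported as an indirect effect, with an equal and opposite spurious direct effect.

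The setting makes this plausible. SoCT and PHQ-9 are measured at the same visits, and nothing requires the skill change to precede the mood change. The treating therapist rates homework compliance, and SoCT has a therapist version, so a patient improving for other reasons may also be rated as more skilled.

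The planned checks cannot show the problem. A one-mediator model with all three paths is saturated, so its fit indices are perfect however strong the confounding. Robust estimation and the bootstrap deal with distributional shape. The reported interval reflects sampling error only. Mediation is in the trial's title, so readers will look for this result.

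**Working it through.** **1. The plan's own figure.** Sample Size Justification: d = 0.50, alpha .01, power 0.80, 96 per group. A two-sided two-sample t calculation gives 95.1 per group, so 96; power at 96 is 0.805. A one-sided test (normal approximation) would need only 81, so the level is taken as two-sided. With 28% attrition, 96 / 0.72 = 133.3, so 134. The figures reproduce and are not in dispute.

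**2. Inputs.**
- From the plan: 96 per arm, level .01, SoCT design effect 0.50.
- Assumed: the 0.50 applies in SD units of mediator change; the true mediator-to-mood effect is zero; mediation is declared when both paths have p < .01; the residual correlation rho between mediator change and mood change, from a common cause, is 0, 0.1, 0.2 or 0.3. The documents give no value for rho.

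**3. Size of the spurious effect.** With both residual SDs equal to 1 and true b = 0, the fitted slope has expectation rho, so the indirect effect is a × rho: 0.5 × 0.1 = 0.05, 0.5 × 0.2 = 0.10, 0.5 × 0.3 = 0.15 SD.

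**4. In PHQ-9 points.** At an SD of 4.0 these are 0.2, 0.4 and 0.6 points. The plan's 4.0 is for another quantity: "standard deviations on the order of ~4.0 have been reported for PHQ-9 total scores post-therapy". With equal SDs at both visits, the SD of change is 4.0 × √(2(1 − r)), which is 4.0 only if the pre-post correlation r is 0.5. At r = 0.7 it is 3.1 and at r = 0.3 it is 4.7, so 0.15 SD is about 0.5 to 0.7 points.

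**5. How often mediation is falsely declared.** The two path tests are close to independent, so the rate is about 0.805 × P(b-path significant). For a correlation adjusted for arm, Fisher's z has standard error 1/√(192 − 4) = 0.0729.

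| rho | z / SE | P(b-path p < .01) | × 0.805 | Simulated, both p < .01 | Simulated, 99% interval for a × b |
|---|---|---|---|---|---|
| 0 | 0 | 0.010 | 0.8% | 0.8% | 0.8% |
| 0.1 | 0.1003 / 0.0729 = 1.38 | 0.115 | 9.3% | 9.1% | 8.9% |
| 0.2 | 0.2027 / 0.0729 = 2.78 | 0.581 | 46.7% | 46.8% | 45% |
| 0.3 | 0.3095 / 0.0729 = 4.24 | 0.952 | 76.6% | 75.7% | 78% |

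The simulations used 5,000 and 3,000 trials per setting. The last column shows that the result does not depend on the joint-test rule.

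**6. When it does not arise.** With a = 0, the rate at which the 99% interval excludes zero was 0.0% to 1.6% for rho from 0 to 0.5. The error needs a real app effect on the mediator.

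**7. What a measured covariate can do.** At rho = 0.3, adjusting for a covariate that carries 25%, 50%, 75% or about 100% of the variance of the common cause lowers the 78% to 67%, 40%, 11% or 1.1%.

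**8. How a tipping value reads.** For an illustrative within-arm correlation of 0.30, the lower 99% limit is tanh(0.3095 − 2.576 × 0.0729) = 0.12. A common-cause correlation of about 0.12 would bring the limit of the b-path to zero; 0.30 would bring the estimate itself to zero.

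**The case against.** A reader might infer that the plan has no check at all for common causes. The documents do not support that. The clause under Preliminary Analyses applies across aims and, with good covariates, could help a great deal (step 7). But it names no variable, is framed around group imbalance and predictors of the dependent variables, is not carried into the mediation section, and cannot reach unmeasured causes. It is a partial safeguard.

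The plan also uses change scores, which remove additive, time-stable causes of level. That narrows the threat to common causes of change, but those are the ones at issue here.

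The size is conditional, and this stands. The correlations are assumed. The plan states no rule for declaring mediation. The 0.50 is a SoCT figure, and the documents give no effect size for the compliance rating or the homework count. Even 0.6 points is 30% of the plan's 2.0-point meaningful difference (0.6 / 2.0). Confounding can also run the other way and mask mediation.

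Finally, the aim is worded as exploratory, and the criticism applies to any mediation analysis with an unrandomized mediator. That limits its weight. It does not make the reported interval reflect confounding.

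**Conclusion.** The point holds as a gap in one secondary, exploratory analysis. Secondary Aim 1 pre-specifies no mediator-outcome confounders and no sensitivity analysis for unmeasured ones, and the general covariate clause and the change scores do not close the gap. If the app truly moves the mediator by 0.5 SD, 96 per arm are analysed and skills have no effect on mood, modest residual correlations of 0.1 to 0.3 are enough to raise false mediation from about 1% to between 9% and 76%.

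It would go too far to infer that the trial will report false mediation, or that the primary comparisons are compromised. The true correlation is unknown, the error needs a real app effect on the mediator, and the primary analyses and sample size do not use the mediation model. Because the correlation is unknown, a sensitivity analysis is a better remedy than any single correction.

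**What to change.** In the Analysis Plan for Secondary Aim 1, directly after the sentence on total, indirect and direct effects, add:

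- Each simple one-mediator model will be refitted in Mplus with the residual correlation between the mediator and PHQ-9 equations fixed at 0, ±0.1, ±0.2 and ±0.3.
- The indirect effect and its 99% interval will be reported at each value, with the value at which the estimate reaches zero and the value at which the interval limit does. If either lies beyond ±0.3, the grid will be extended.
- Any mediation conclusion will be worded as conditional on common causes being weaker than that value.

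Limit this to the simple models. The multiple-mediator and growth models would need several residual correlations at once.

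Cost: seven fits per mediator, so 7 × 4 = 28 for the four mediators named, with longer runs if bootstrapped, and one extra table. No new data or software are needed. The downside is a possibly more cautious conclusion for an exploratory aim.
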